# Figure 1. Examples of Blinded Labels

### **Holding Box Labels**

Box Label

MAPS Study# MP-8

Investigational Product: MDMA

Dose: XXXmg Lot #: XXXXX

Administer as per protocol

Caution-Limited by Law to Investigational Use Only

# **Stage 1 Primary Container Labels**

MAPS Study MP-8	MAPS Study # MP-8
Experimental Session #	Experimental Session #
Container # XXX	125 & 62.5mg
Subject #	Container # XXX
Administer as per protocol	Subject #
Investigational Use Only	Administer as per protocol
	Investigational Use Only

# **Stage 1 Inner Envelope Labels**

#### Blinded Blinded

Stage 1	Container # XXX	Stage 1	Container # XXX
INITIAL DOSE		SUPPLEMENT	TAL DOSE
Subject #	Ex. Ses #	Subject #	Ex. Ses #

#### Open Label Session 3

		_		
Stage 1	Open Label 125mg		Stage 1	Open Label 62.5mg
INITIAL DOSE			SUPPLEMEN	NTAL DOSE
Subject #	Ex. Ses #		Subject #	Ex. Ses #

### **Stage 2 Primary Container Labels**

Open Label Session 1

Open Label Session 2 or 3

Open Label Session 3

MAPS Study # MP-8
Stage 2
100mg & 50mg MDMA
Lot # XXX
Container # XXX
Subject #
Experimental Session #1
Administer as per protocol Investigational Use Only

MAPS Study # MP-8
Stage 2
100+25mg & 50+12.5mg MDMA
Lot # XXX
Container # XXX

Subject #\_
Experimental Session #\_
Administer as per protocol Investigational Use Only

#### **Stage 2 Inner Envelope Labels**

### Open Label Session 1

Stage 2	Open Label 100mg
INITIAL DOSE	
Subject #	Ex. Ses # 1

### Open Label Session 2 or 3

Stage 2 INITIAL DOSE	Open Label 100mg
Subject #	Ex. Ses #
Stage 2 INITIAL DOSE	Open Label 25mg
Subject #	Ex. Ses #

# Open Label Session 1

Stage 2	Open Label 50mg	
SUPPLEMEN	TAL DOSE	
Subject #	Ex. Ses # 1	

## Open Label Session 2 or 3

Stage 2	Open Label 50mg						
SUPPLEMENTAL DOSE							
Subject #	Ex. Ses #						
Stage 2	Open Label 12.5mg						
SUPPLEMENTAL DOSE							
Subject #	Ex. Ses #						

The IP for each experimental session will be packaged in one primary container, labeled with a unique container number, protocol number, drug name, lot number, sponsor name, experimental session number, stage, and a statement that the drug is restricted to clinical trial use only. All drug labels will comply with federal and state regulations and will be provided in English. The initial and supplemental dose will be packaged in separate labeled "inner envelopes" within the primary container. There will be one primary container per subject per experimental session. The sponsor randomization monitor will oversee the process of blinded drug packaging conducted by the pharmacist according to the randomization list. This list will not be shared with any blinded site or sponsor staff. The pharmacist and randomization monitor will be the only staff who are unblinded.

#### 4.4 MDMA Accountability

Forms will be provided to track drug accountability and administration throughout the study. Blinded drug accountability and administration logs will be reviewed during routine monitoring visits. MDMA will be handled in accordance with all state and federal regulations and forms pertaining to the use of controlled substances, and forms will be maintained by the Schedule 1 License Holder.

Each primary container label will contain a unique container number for the drug assigned to a single experimental session. The container numbers will be used to track drug administration in the Source Record and the drug administration log. The web-based randomization system will enable tracking of blinded primary containers for drug accountability purposes.

## 4.5 MDMA Storage and Handling

MDMA is a Schedule 1 compound and will be stored and handled in compliance with relevant Federal and State regulations. In accordance with DEA requirements, the Clinical Investigator will be responsible for storing and dispensing the MDMA. It will be stored in a safe mounted to the floor that has been inspected and approved by the DEA for this purpose. Only the Clinical Investigator with the Schedule 1 license will have the combination to the safe. The room in which the safe is mounted has an alarm system and will be locked whenever the CI or his staff are not present.

All doses administered will be recorded on the appropriate accountability and administration logs. Only the initial dose is required to be given at each experimental session. Supplemental doses are provided for each experimental session but are optional to use. In addition, the clinical titration doses with corresponding supplemental dose are provided in Stage 2 session 2 and 3 and their use is optional.

The Schedule 1 License Holder will dispense the appropriate container number for each experimental session. If an optional dose is not administered the unused capsules will be kept in their respective inner envelopes inside of the primary container in the safe for drug accountability.

Investigational product will only be removed from the safe for one subject at a time at the time of the session and the MDMA will not leave the premises. MDMA will be administered orally with a glass of water. All doses administered will be recorded on the appropriate accountability logs. Records pertaining to the use of Schedule 1 compounds will be maintained in accordance with relevant Federal and State Regulations. They will be kept separate from other records and will be maintained in a locked cabinet in a locked office with an alarm system.

# **4.6 MDMA Stability**

Complete details on the chemistry, manufacturing and control of the MDMA to be used are described in Drug Master file (DMF) # 6293. As described in that file, MDMA was prepared for human consumption in 1985 by [name]., Dept. of Medicinal Chemistry and Pharmacology, Purdue University. The identity and purity of this MDMA was confirmed using High Performance Liquid Chromatography (HPLC) in 1997 as described in DMF # 6293 and was found to be 99.87% pure. On August 12, 2002, Chemic Laboratories reanalyzed the MDMA at the request of the sponsor prior to starting MAPS' first U.S. pilot study of MDMA-assisted psychotherapy in people with PTSD. The analysis found the MDMA to be more than 99.7% pure. A more recent analysis performed by [name] at the request of researcher [name] on February, 2006, continued to find a high degree of purity. This analysis found the MDMA in question to be 99.9% pure. This MDMA was used in an investigation of MDMA-assisted psychotherapy that took place in the U.S. with drug administration ending in 2008, and it was also used in non-sponsor supported study in 2006[76].

### 5.0 Protocol Design

This randomized, triple-blind study will examine the safety and efficacy of MDMA-assisted psychotherapy with 30, 75 or 125 mg MDMA in twenty-four veterans, firefighters and police officers diagnosed with chronic, treatment-resistant PTSD arising from their service. These participants will ideally, but not necessarily, include twelve men and twelve women. Supplemental doses of half the initial dose may be administered between 1.5 and 2.5 hours after the initial dose was administered.

Prior to undergoing the first MDMA-assisted (experimental) session, all participants will undergo three 90-minute preparatory non-drug psychotherapy sessions with a male and female co-therapist team. Stage 1 of the study will consist of two blinded experimental sessions and, for the full dose group, one open-label experimental session, each lasting six to eight hours and scheduled three to five weeks apart. The study will be unblinded after the second experimental session in Stage 1, which constitutes the primary endpoint assessment. After unblinding, medium dose and low dose subjects will have the opportunity to continue to open-label Stage 2, unless they meet any exclusion criteria for study participation and full dose subjects will complete the third open-label experimental session. All subjects will complete a long-term follow-up visit 12 months after their final experimental session. All psychotherapy sessions may be recorded to audio and video. In the first open-label experimental session in Stage 2, subjects will receive 100mg with an optional supplemental dose of 50mg. In the second and third open-label experimental session in Stage 2, subjects will receive one of two active doses of MDMA that are clinically titrated by the CI. Experimental sessions will otherwise follow the same sequence of events after a single preparatory session. (See Time and Events Table).

A co-therapist team will perform all non-drug and MDMA-assisted psychotherapy sessions in their outpatient office. Participants will complete the SOCQ, a measure of alterations in consciousness related to mystical experiences, during the period of time between the end of each MDMA-assisted psychotherapy session and before they leave the treatment facility the next day. Participants will remain at the study site overnight accompanied by an attendant. Participants will undergo three integrative psychotherapy sessions after each experimental session, with the first integrative session occurring on the day after the experimental session.

A blinded independent rater, who will not be present during any psychotherapy sessions, will assess participant PTSD symptoms with CAPS, symptoms of depression with BDI-II, posttraumatic growth with PTGI, global functioning with GAF, sleep quality with PSQI, and dissociation with the DES-II. Changes in personality traits will be assessed via NEO-PI. Outcome assessments will be done at baseline, at the primary endpoint one month after the second experimental session, two months after the third open-label experimental session and at the 12-month follow-up and at equivalent points in Stage 2.

When each subject completes the evaluation at the primary endpoint, the blind will be broken for that subject. Participants who had been assigned to receive low dose or medium dose MDMA will subsequently have the opportunity to enroll in the open-label study arm, or "Stage 2." Stage 2 must start within a maximum of 5 months after the participant finishes Stage 1. The open-label study arm will follow a similar sequence of events and procedures, except that there will be a single preparatory session, and all three MDMA-assisted psychotherapy sessions will be open-label. Subjects will receive an initial dose of 100 mg MDMA in the first experimental session, and one of two active doses of MDMA that are clinically titrated by the CI during the second and third open-label experimental sessions that will otherwise follow the same sequence of events (See Time and Events Table). Outcome measures except for the NEO PI will be repeated one month after the second Stage 2 experimental session, and all outcome measures will be repeated at the end of Stage 2.

The study will conclude with a one-year follow-up occurring 12 months after the final experimental session of Stage 1 for participants who received full dose MDMA or who elected not to enroll in Stage 2 after receiving either the medium or low doses in Stage 1. Subjects who enrolled in Stage 2 will have their final follow-up 12 months after the final open-label experimental session. Outcome measures will be repeated at the 12-month follow-up, as well as a questionnaire concerning self-reported long-term effects of study participation.

An interim analysis may be performed before all participants have completed the 12-month follow-up. The interim data analysis may be conducted for safety and efficacy.

Sub-studies in a select group of subjects in this study may be conducted for exploratory purposes. Subjects will complete a separate consent process if they chose to participate in these studies.

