#### 5.3.1 Inclusion Criteria

Individuals eligible to be enrolled into this protocol are participants who:

- 1. Meet DSM IV criteria for current PTSD with a duration of 6 months or longer resulting from traumatic experience during military service;
- 2. Have a CAPS score of 50 or higher, indicating moderate to severe PTSD symptoms;
- 3. Have had at least one unsuccessful attempt at treatment for PTSD with medication, such as an SSRI, SNRI, or mirtazapine, or one unsuccessful treatment with any form of psychotherapy for which there exists a controlled trial indicating efficacy in the treatment of PTSD. This includes cognitive-behavioral therapy

(including exposure therapy), stress inoculation training, including anxiety management, insight-oriented psychotherapy, and EMDR.

OR who discontinued treatment due to either:

- Inability to tolerate psychotherapy for PTSD (e.g. persistent "overengagement" when attempting Prolonged Exposure Therapy) or
- Inability to tolerate psychopharmacology for PTSD due to treatment-emergent side effects;

Treatment will be deemed to have been unsuccessful if the participant continues to meet criteria for current PTSD following the treatment.

- 4. Are at least 18 years old;
- 5. If in ongoing psychotherapy at the time subjects are recruited into the study, participants may continue to see their outside therapist during the course of the study. Participants must sign a release for the investigators to communicate directly with their therapist. Subjects may not change therapists, increase the frequency of therapy or commence any new type of therapy until after the evaluation session 2 months after the final experimental session. Subjects who do not live within reasonable driving distance of the study site (equal to or less than an estimated two hours' drive from the study site) must have a therapist in the area in which they live whom they can call on for support and evaluation if necessary;

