#### **5.3.2 Exclusion Criteria**

Individuals not eligible to be enrolled into this protocol are those who:

- 1. Are pregnant or nursing, or are women of child bearing potential who are not practicing an effective means of birth control;
- 2. Have a history of, or a current primary psychotic disorder, bipolar affective disorder type 1 or, dissociative identity disorder;
- 3. Have evidence or history of coronary artery disease or cerebral or peripheral vascular disease, hepatic disease with abnormal liver enzymes, or any other medical disorder judged by the investigator to significantly increase the risk of MDMA administration;
- 4. Have hypertension using the standard criteria of the American Heart Association (values of 140/90 or higher assessed on three separate occasions [77]), unless their hypertension has been successfully treated and is currently well-controlled on antihypertensive medicines, In this case subjects with well-controlled hypertension may be enrolled if they pass additional screening to rule out underlying cardiovascular disease (see "Methods");
- 5. Have liver disease with the exception of asymptomatic subjects with Hepatitis C who have undergone additional evaluation (see "Methods"). Subjects with Hepatitis C may be enrolled if they have received appropriate screening (see "Methods");
- 6. Have history of hyponatremia or hyperthermia;
- 7. Weigh less than 48 kg;
- 8. Would present a serious suicide risk, as determined through psychiatric interview, responses to C-SSRS and through the clinical judgment of the investigator, or who, in the judgment of the investigator, are likely to require hospitalization during the course of the study;

- 9. Would present a serious risk to others as established through clinical interview and contact with treating psychiatrist;
- 10. Have used "Ecstasy" (material represented as containing MDMA) more than five times within the last 10 years or at least once within 6 months of the MDMA session;
- 11. Require ongoing concomitant therapy with a psychotropic drug;
- 12. Meet Diagnostic and Statistical Manual of Mental Disorders (DSM)-IV criteria for active substance abuse or dependence for any substance save caffeine or nicotine in the past 60 days;
- 13. Are not able to give adequate informed consent;
- 14. Have any current problem or a history of substance abuse which, in the opinion of the investigator or medical monitor, might interfere with participation in the protocol.

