A =First Integrative session is 1 day after exp session B = At least 24 hrs prior to 1st exp. session C =Approximately 6 hours post MDMA D =At the beginning of the session E =As needed F=Approximately every 60 minutes G =Given on 2nd preparatory session after meds are tapered (V3) H = Only for subjects starting Long term Follow up and not going to Stage 2 I =For 7 days post Exp. Session, C-SSRS D2 and D7 of calls only, General well being for all 7 days J =Subjects in the medium or low dose group will not have visits 14-18, but will instead move onto Stage 2. K= On the day of the 1st integrative session following the Exp. Session I =CAPS may be videotaned M=First preparatory session (V2) may happen at the time of screening, before enrollment. N= Full dose subjects only. O= Only in subjects with pre-existing timitus and/or chronic pain

Table4.Stage2Time&Events	Preparatory	Experiment	tal Session 1	on 1 Experimental Session 2			Experimen	tal Session 3	Follow-Up		Long Term Follow-Up
Visit #	V19*	V20	V 21,22,23	V24	V 25,26,27	V28	V29	V 30,31,32	V33		1 Year Follow-up
Type of Visit	Preparatory Session	Experimental Session 1	Integrative Sessions	Experimenta 1 Session 2	Integrative Sessions	Secondary endpoint	Experiment al Session 3	Integrative Sessions	End of Stage 2 & Outcome		Follow-Up & Outcome
Visit Timing or Study day or Window	Within maximum of 5 months of V13*	After V19	Before V24 A	3-5 weeks post V20	Before V28 A	1 month post V24, beforeV29	3-5 weeks post V24	Before V33	May happen over > 1 day 2 months post V29		May happen over > 1 day. One Year post V14 or V29
Confirm Informed Consent	X										
Confirm Inclusion/Exclusion	X										
Enrollment in Stage 2	X										
Collect Concomitant Medication	X	X	X	X	X	X	X	X	X	7	X
Record to Audio/Video	X	X	X	X	X	$X^{H}$	X	X	$X^{H}$	Stage	
General Well-Being	X	X	X	X	X		X	X	X	Sta	
Drug Screen		X		X			X			or ,	
Pregnancy Screen (if applicable)		X		X			X			_	
CAPS, GAF, BDI-II, PTGI, PSQI, DES-II (IR)	Use V13*					X			X	Stage	X
NEO PI with Ind. Rater	Use V13*								X	er	X
C-SSRS	X	X C, D, E	$X^{G}$	X C, D, E	X G		X C, D, E	X G	X	after	X
Administer IP Drug + Therapy, SOCQ		X		X			X			dn	
Monitoring of BP, Pulse and Temp.		X		X			X			Follow	
SUD		X D, F		X D, F			X D, F			o	
Overnight Stay		X		X			X				
Integrative Therapy Session			X		X			X		Term	
7 days Integrative Telephone Contact			X G		X G			X G		Ī,	

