## 6.2.7 Evaluation at Primary Endpoint & Unblinding (Visit 13)

The primary endpoint evaluation in Stage 1 will occur one month after the second blinded experimental session. This visit will consist of two meetings that may be completed on separate days, one with the independent rater and the other with the therapists. The blinded independent rater will administer: CAPS to assess PTSD symptoms, BDI-II to assess depression symptoms, GAF to assess general psychological function, PTGI to assess post-traumatic growth (in reference to start of the study), PSQI to assess sleep quality, DES-II to assess dissociation symptoms and NEO PI to assess personality. The blinded independent rater will provide their belief of the subject's condition assignment.

After completing all assessments and measures with the independent rater, the subject will meet with the therapists for approximately 30 minutes. Following the visit with the independent rater the blind will be broken for the subject's condition assignment. The independent rater will remain blind to condition assignment at this time. The therapists will assess suicidality with the C-SSRS. The visual analog scale will be used to collect

changes in subjects who have pre-existing tinnitus and chronic pain symptoms.

If the subject had been assigned to receive medium dose or low dose MDMA, the therapists will discuss continuation to Stage 2. Low and medium dose subjects will not complete the third experimental session and associated integrative sessions in Stage 1. Participants who decline continuing to Stage 2 will complete the Responses to Research Participation Questionnaire (RRPQ). If participants had been assigned to the full dose condition in Stage I, they will provide their perceptions of experimental sessions at this point. The therapists will discuss scheduling the third open label full dose experimental session and integrative sessions.

Adverse Events and medications will be collected as described in Sections 8 and 9 of the protocol.

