# 6.2.10 Open-Label Study Segment for Low Dose and Medium Dosage Participants ("Stage 2")

Participants assigned to receive low dose or medium dose MDMA during Stage 1 will undergo three open-label MDMA-assisted psychotherapy sessions that follow a course and schedule similar to Stage 1 for the full dose group except that participants will

undergo one instead of three introductory sessions. After confirming consent and eligibility criteria, participants continuing to Stage 2 will meet with both investigators conducting psychotherapy for a single review and preparatory psychotherapy session before the first open-label MDMA-assisted psychotherapy session. If more than 8 weeks have passed since the primary endpoint, all measures will be repeated for a new baseline prior to the first open-label experimental session. Experimental sessions will be conducted according to procedures described in Section 6.2.3. During the first experimental session, subjects will receive a 100 mg initial dose of MDMA and may receive a 50mg optional supplemental dose of MDMA. At the beginning of each of the second and third experimental sessions, the co-therapists, in consultation with the subject, will decide whether to administer an initial dose of 100 mg or 125 mg initial dose of MDMA. If a 100mg initial dose of MDMA is selected, an optional supplemental dose of 50mg MDMA may be administered. If a 125mg initial dose of MDMA is selected, an optional supplemental dose of 62.5mg MDMA may be administered. If the PI decides not to administer the optional supplemental dose and/or the optional clinical titration dose in a given experimental session, the unused capsules will be kept in their respective inner envelopes inside of the primary container in the safe.

Integrative sessions will be conducted according to procedures described in Sections 6.2.4 and 6.2.6. Phone calls will be conducted according to procedures described in Section 6.2.5.At the secondary endpoint based on procedures described in Section 6.2.7, the Independent Rater will administer the CAPS and GAF. Subjects will complete the BDI-II, PSQI, PTGI (in reference to the start of the study), and DES-II.Administration of the CAPS may be recorded to video.

Investigators will follow the most recent treatment manual in all matters relating to the Open-Label Stage 2 experimental psychotherapy sessions

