#### Crossover Subject Analyses

Data from subjects assigned to the low and medium dose groups, i.e. ‘crossover population,’ will be analyzed by within-subject t-tests comparing difference scores from primary endpoint in Stage 1 to secondary endpoint in Stage 2 (Table 3 and 4). The following measures total scores will be analyzed in this fashion: CAPS, PTGI, BDI-II, GAF, PSQI, DES-II, and NEO PI.

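### The Stage 2 entry rule differs between Protocol 5.0 and Table 4, leaving open whether current PTSD and CAPS of 50 or higher are re-applied, and the SAP crossover test ignores the repeated Stage 2 baseline

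*Protocol*

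**What the plan says.** **Entry to Stage 2.**

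- Protocol 5.0: low- and medium-dose subjects may continue after unblinding "unless they meet any exclusion criteria for study participation". Inclusion criteria are not mentioned.
- Protocol Table 4 (Stage 2 Time & Events), and its copy in SAP 4.1: the V19 column is marked for "Confirm Inclusion/Exclusion".
- Protocol 6.2.10: "After confirming consent and eligibility criteria, participants continuing to Stage 2 will meet with both investigators conducting psychotherapy". It does not say which criteria, and it restates no threshold.
- Protocol 6.2.7: "If the subject had been assigned to receive medium dose or low dose MDMA, the therapists will discuss continuation to Stage 2". No severity condition is attached.

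**The criteria.** Inclusion criterion 1 in Protocol 5.3.1 begins "Meet DSM IV criteria for current PTSD with a duration of 6 months or longer", and criterion 2 is "Have a CAPS score of 50 or higher, indicating moderate to severe PTSD symptoms". The list in 5.3.2, introduced by "Individuals not eligible to be enrolled into this protocol are those who", has 14 items. None concerns a CAPS score or loss of the PTSD diagnosis.

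**The Stage 2 starting score.** Table 4 takes the V13 scores as the starting values at V19. Its footnote and Protocol 6.2.10 require the measures to be repeated when more than 8 weeks have passed since V13; 6.2.10 calls the result a new baseline.

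**The analysis.** SAP 8.9.2.2 specifies "within-subject t-tests comparing difference scores from primary endpoint in Stage 1 to secondary endpoint in Stage 2". SAP 8.1 defines the crossover population as those who completed both stages.

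**The concern.** Two texts give different conditions for the same decision. The conditions on which they differ include the score that later serves as the start of the crossover comparison. With 6 low-dose and 6 medium-dose subjects, at most 12 can cross over, so a few ambiguous entries change the population materially.

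If the CAPS threshold is re-applied to the V13 score, the subjects admitted have been selected for a high value of it, and part of any fall to the next rating is regression to the mean. If it is not re-applied, that component is absent. A reader of the results could not tell which situation applies.

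The second difficulty does not depend on the entry rule. The protocol goes to the trouble of a new baseline after a long gap, but the SAP test does not use it. For those subjects, change from V13 would include whatever happened between V13 and the repeat, an interval of up to 5 months without study drug.

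**Working it through.** **1. The texts side by side.** Take a medium-dose subject with a V13 CAPS of 40, no exclusion criterion met, and V19 within 8 weeks.

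| Text | Result for this subject |
|---|---|
| Protocol 5.0 | Enters |
| Protocol 6.2.7 | Continuation is discussed; no severity condition |
| Protocol 6.2.10 | Undetermined: depends on what its eligibility criteria cover |
| Table 4 and SAP copy, read literally | Refused under inclusion criterion 2 |

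No sentence in either document resolves the difference.

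**2. Who would be refused if criteria 1 and 2 were re-applied.** Only subjects scoring below 50 or without current PTSD. A subject with a baseline of 50/0.7 = 71.4 or more can fall by 30% and still score at least 50. A fall from 90 to 55 is 35/90 = 39%, and that subject still meets criterion 2.

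**3. Size of the selection effect, if the threshold is re-applied to V13.** The documents give no V13 mean, SD or retest correlation r, so these are assumed. With a normal distribution of mean m and SD s, and a = (50 − m)/s:

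- share below 50 = Φ(a)
- mean of those admitted = m + s·φ(a)/(1 − Φ(a))
- apparent fall with no true change = (1 − r) × (mean admitted − m)

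For m = 60, s = 25, r = 0.8: a = −0.4; Φ(a) = 0.345; mean admitted = 60 + 25 × 0.368/0.655 = 74.0; apparent fall = 0.2 × 14.0 = 2.8 points.

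| V13 mean (SD 25) | Share below 50 | Admitted of 12 | Fall, r = 0.9 | r = 0.8 | r = 0.6 |
|---|---|---|---|---|---|
| 50 | 0.50 | 6.0 | 2.0 | 4.0 | 8.0 |
| 60 | 0.345 | 7.9 | 1.4 | 2.8 | 5.6 |
| 70 | 0.212 | 9.5 | 0.9 | 1.8 | 3.7 |

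**4. Effect on the paired t-test.** Each setting was simulated 40,000 times with 12 candidates, no true change and a two-sided 0.05 test. Samples with fewer than 3 subjects admitted were dropped. With SD 25 and r = 0.8, the false-positive rate was 0.083, 0.072 and 0.062 at V13 means of 50, 60 and 70. Over means of 50 to 70, SD 20 to 25 and r from 0.6 to 0.9, the range was 0.053 to 0.123. With no threshold and all 12 entering it was 0.048 to 0.052.

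**5. The repeated baseline.** Protocol 6.2.10 and the footnote to Table 4 (also in the SAP copy) create a second pre-treatment score when the gap exceeds 8 weeks. SAP 8.9.2.2 names only the Stage 1 primary endpoint as the start of the crossover change. SAP 8.5 defines baseline as the screening/baseline visit (with an exception only for the C-SSRS) and gives no Stage 2 baseline. The repeat is therefore collected but has no place in the test. Its effect cannot be sized from the documents.

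**The case against.** The best case against is that the CAPS threshold was never meant to be re-applied. Protocol 5.3 ties it to the baseline evaluation. Protocol 5.0 recognises low- and medium-dose subjects who enrol in Stage 2 and those who choose not to, with no category for subjects refused. Sections 6.2.7 and 6.2.9 offer Stage 2 by assigned dose and choice. Most inclusion items are undertakings, such as medication limits, birth control and a contact person, which could sensibly be re-confirmed without re-testing severity. Section 6.2.3 describes confirming eligibility at drug sessions by urine drug and pregnancy screens.

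Much of this stands: re-application is the literal reading of one table row and its copy, not an express rule. But it does not settle the matter. The row names inclusion without limiting it to some items, and the drug and pregnancy screens are not marked at V19, so they cannot be what that row means.

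The consequence is also limited. The comparison is open-label and uncontrolled, and SAP 3.2 lists its objective among the exploratory ones, although SAP 8.9.2.2 treats it as a secondary efficacy analysis. Entry is elective and the population is completers, so there is selection under either rule. In the m = 60 example with r = 0.8, the variance of change among those admitted is 0.2² × 287 + 625 × 0.36 = 236 (287 being the variance of the admitted scores), an SD of 15.4. With 8 subjects the standard error is 15.4/√8 = 5.4, so a 2.8-point shift is about half a standard error.

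Three stronger readings are tempting and not supported. A reader might infer that Stage 1 improvers in general are barred, or that the crossover set consists of non-responders; step 2 of the working shows otherwise. A reader might also infer that therapists decide entry knowing the V13 CAPS. Section 6.2.7 has the independent rater administer the CAPS and then breaks the blind for assignment; it does not say that therapists receive the score.

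**Conclusion.** The entry rule is inconsistent on the page, and neither document says whether inclusion criteria 1 and 2 apply again at V19. That much needs no assumption.

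The statistical consequence is conditional. Only if the CAPS threshold is re-applied to V13 does the crossover test start from the selecting score. The resulting regression to the mean is then about 2 to 4 CAPS points for a V13 mean of 50 to 70, SD 25 and r = 0.8, and 0.9 to 8.0 points if r runs from 0.9 down to 0.6. All these inputs are assumed. The calculation also takes every admitted subject to enter and complete Stage 2.

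The failure of SAP 8.9.2.2 to use the repeated baseline stands under either entry rule. The randomized comparison at V13 is untouched. The point is worth correcting because it is cheap and because Protocol 3.2 lists Stage 2 against Stage 1 as a secondary objective; it does not threaten the trial's main result.

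**What to change.** 1. Reconcile Protocol 5.0, Protocol 6.2.10 and Table 4 with its SAP copy so that they state one Stage 2 entry rule. Say whether inclusion criteria 1 and 2 are re-applied at V19 and, if so, whether on the V13 score or on the repeat. The choice of rule is for the sponsor.
2. In SAP 8.9.2.2, start the crossover change from the repeated measures where the gap of more than 8 weeks required them, and from V13 otherwise.
3. In the same section, report the low- and medium-dose subjects who did not cross over, with the reason (not eligible or declined) and V13 CAPS. SAP 8.0 already puts unanalysed data in listings, so the scores will exist; what is missing is a planned account of who did not cross over and why.
4. Only if the threshold is re-applied, state that change measured from the score used for selection includes regression to the mean.

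The cost is a sentence in each place that states the entry rule, an edit to one SAP paragraph, and one listing. No new data are needed.
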